Title

Observational Study to Assess the Effectiveness of a Smartphone Application in Enhancing Adoption of the 2024 KDIGO CKD Guideline.

1. Background and Rationale

Chronic Kidney Disease (CKD) affects millions of individuals worldwide, and adherence to clinical guidelines is critical for managing the disease effectively. The 2024 KDIGO CKD Guidelines provide comprehensive recommendations for the diagnosis and management of CKD. However, implementation of these guidelines remains a challenge. This study aims to evaluate the effectiveness of a smartphone application designed to assist doctors and patients in following the 2024 KDIGO CKD guidelines.

2. Objectives

Primary Objective

To assess the effectiveness of a smartphone application in enhancing the adherence to the 2024 KDIGO CKD guidelines over a 18-month period. This includes recommendations on lifestyle modification as well as optimal disease modifying medications to reduce the loss of kidney function and cardiovascular risk over time.

Secondary Objectives

- To evaluate changes in clinical parameters (e.g., blood pressure, eGFR, urinary protein excretion) over the study period.
- To assess patient satisfaction and engagement with the smartphone application.
- To determine the impact of the application on the quality of life of CKD patients.

3. Study Design

This is an observational, prospective cohort study. Participants will be assessed at baseline and at intervals over 18 months.

4. Study Population

Inclusion Criteria

- Adults aged ≥ 16 years.
- Diagnosed with CKD stages 1-5.
- Owns a smartphone and is capable of using mobile applications.
- Provides informed consent.

Exclusion Criteria

- Inability to provide informed consent due to cognitive impairment.

5. Study Procedures

Baseline Visit

1. Obtain informed consent.
2. Collect demographic and medical history.
3. Conduct baseline measurements:
 - Blood pressure
 - Serum creatinine
 - Estimated Glomerular Filtration Rate (eGFR)
 - Urine Albumin-to-Creatinine Ratio (ACR)
 - Weight, height, BMI
4. Collect information on lifestyle factors:
 - Diet
 - Physical activity level
 - Smoking status
 - Alcohol consumption
5. Assist participant in downloading and setting up the smartphone application.

Follow-Up Visits

Participants will be assessed at 3, 6, 9, and 12 months. At each visit:

1. **Collect follow-up measurements:**
 - Blood pressure
 - Serum creatinine
 - eGFR
 - Urine ACR
 - Weight, height, BMI
2. **Review application usage data:**
 - Number of logins per week
 - Frequency of viewing educational materials
 - Frequency of logging health data
 - Number of reminders received and responded to
3. **Assess adherence to KDIGO guidelines:** *Disease modifying medication*
prescription including ACE inhibitors and ARBs, SGLT2 inhibitors, GLP-1 analogues, Finerenone and endothelial antagonists.
 - *Blood pressure control* versus targets recommended by the KDIGO Guidelines.
 - Dietary recommendations
 - Physical activity recommendations
 - Attendance at medical appointments
4. **Collect patient feedback on the application:**
 - Ease of use (scale 1-5)
 - Usefulness of educational materials (scale 1-5)

- Effectiveness of reminders (scale 1-5)
 - Overall satisfaction (scale 1-5)
 - Suggestions for improvement
5. **Quality of life assessed in patients** using a validated questionnaire (e.g., POS-S-Renal).

6. Outcome Measures

Primary Outcome

- Adherence to the 2024 KDIGO CKD guidelines, measured by changes in adherence scores from baseline to 12 months in the variables specified above (recommended medications and lifestyle modifications).

Secondary Outcomes

- Changes in clinical parameters (blood pressure, serum creatinine, eGFR, urine ACR).
- Patient satisfaction and engagement with the application.
- Quality of life assessed in patients being managed as part of the conservative care pathway using a validated questionnaire (e.g., POS-S-Renal).

7. Data Management and Analysis

Data Collection

Data will be collected using electronic data capture systems. All data will be anonymized and stored securely.

Statistical Analysis

- Descriptive statistics for baseline characteristics and outcome measures.
- Paired t-tests or Wilcoxon signed-rank tests to compare baseline and follow-up measurements.

8. Ethical Considerations

Informed Consent

Written informed consent will be obtained from all participants through the smartphone application.

Confidentiality

Participant confidentiality will be maintained. Data will be anonymized and securely stored.

Ethical Approval

The study protocol has been approved by the hospital ethics committee.

9. Dissemination of Results

The results of the study will be published in peer-reviewed journals and presented at national and international conferences. A summary of the study results will be shared with participants through the smart phone application.

10. Timeline

- **Month 0:** Study initiation and baseline assessments.
- **Months 3, 6, 9:** Follow-up assessments.
- **Month 12:** Final follow-up assessments and data analysis.
- **Months 13-15:** Data analysis and manuscript preparation.
- **Month 16:** Dissemination of results.

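### App satisfaction is asked only at attended visits, and the protocol does not say usage logs are taken regardless of attendance, so both outcomes may look better than they are

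*Protocol*

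**What the plan says.** Section 2 names as a secondary objective "To assess patient satisfaction and engagement with the smartphone application", and Section 6 repeats it as a secondary outcome: "Patient satisfaction and engagement with the application".

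The data come from Section 5, Follow-Up Visits. The list of procedures opens with "Participants will be assessed at 3, 6, 9, and 12 months. At each visit", and everything after it hangs from that line. Item 2 is "Review application usage data"; its measures include "Number of logins per week" and "Number of reminders received and responded to". Item 4 is "Collect patient feedback on the application", made up of 1-5 ratings (ease of use, teaching material, reminders, overall satisfaction) and free suggestions.

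The baseline visit ends with the app being set up and includes no feedback item. No section describes feedback sought outside a visit, an exit questionnaire, or contact with people who stop using the app or stop attending. No section says where usage data are extracted from, for whom, or over what period. Section 7 gives descriptive statistics for outcome measures and fixes no denominator.

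**The concern.** A rating that is requested only at a visit exists only for people who come. Someone who abandons the app and also stops attending gives no low rating, yet that is a person this outcome ought to reveal. Because there is no baseline rating, a participant lost before month 3 contributes no satisfaction data at all. A later analysis plan cannot repair this, since a rating never requested cannot be recovered.

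Two things are at stake. The average at any visit may be too high. The series of averages from month 3 to month 12 may also rise without any individual becoming more satisfied, because less satisfied people have left the denominator.

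For usage the issue is an open instruction. The only operational step in the protocol is a review at the visit. A site that follows it literally could record usage for attenders only, and engagement would then carry the same selection.

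**Working it through.** The protocol states no sample size, attrition rate or expected rating, so there is no figure of its own to reproduce. The inputs below are assumptions, used to show how the bias behaves.

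**Formula.** Let d be the share of enrolled participants missing a visit and g the mean in attenders minus the mean in non-attenders. The full-cohort mean is (1 − d) × attender mean + d × non-attender mean, so

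attender-only mean − full-cohort mean = d × g.

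**Satisfaction, 1-5 scale, d from 0.10 to 0.40.**

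| g (points) | d = 0.10 | d = 0.20 | d = 0.30 | d = 0.40 |
|---|---|---|---|---|
| −0.5 | −0.05 | −0.10 | −0.15 | −0.20 |
| 0 | 0 | 0 | 0 | 0 |
| 0.5 | 0.05 | 0.10 | 0.15 | 0.20 |
| 1.0 | 0.10 | 0.20 | 0.30 | 0.40 |
| 1.5 | 0.15 | 0.30 | 0.45 | 0.60 |

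With attenders 0.5 to 1.5 points higher, the overstatement runs from 0.10 × 0.5 = 0.05 to 0.40 × 1.5 = 0.60 points. It is zero if the groups do not differ, and negative if non-attenders are the more satisfied.

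**Apparent trend.** Hold the full-cohort mean constant and g at 1.0. If d grows from 0.10 to 0.40 between two visits, the attender mean rises by 0.40 − 0.10 = 0.30 points with no change in the cohort.

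**Engagement, only if usage were summarised for attenders alone.** Assume 3 logins per week in attenders and 0.5 in non-attenders.

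| d | Full-cohort mean | Overstatement |
|---|---|---|
| 0.10 | 0.9 × 3 + 0.1 × 0.5 = 2.75 | 3/2.75 − 1 = 9% |
| 0.20 | 0.8 × 3 + 0.2 × 0.5 = 2.50 | 3/2.50 − 1 = 20% |
| 0.30 | 0.7 × 3 + 0.3 × 0.5 = 2.25 | 3/2.25 − 1 = 33% |
| 0.40 | 0.6 × 3 + 0.4 × 0.5 = 2.00 | 3/2.00 − 1 = 50% |

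If the logs of every enrolled participant are analysed, the reported mean is the full-cohort mean and the overstatement is 0 in every row.

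**The case against.** A reader might infer that usage, too, is collected only at attended visits and that both outcomes will be overstated. The documents do not support that.

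- **The wording for usage differs.** Usage is reviewed at the visit, whereas measurements and feedback are collected. Weekly logins and reminder counts are finer than three-monthly visits and read as records the app itself generates. Nothing says they are lost when a visit is missed. This objection stands: for usage, the fault is an unstated extraction rule.
- **The direction of bias is not given.** Attending and using the app are separate behaviours. Visits also cover blood pressure, laboratory measures, medication and quality of life, so someone who drops the app but still attends contributes a low rating and low usage. The population includes CKD stage 5 and a conservative care pathway, so illness or death may explain absence. This also stands, and is why the claim is that the outcomes may be overstated.
- **Setting every leaver to zero logins gives a limit only.** With 60-90% attending, it yields factors of 1/0.9 = 1.11 to 1/0.6 = 1.67. Those are extremes under invented attendance and should not be read as an expected effect.
- **Denominators and missing data may be in the analysis plan.** That plan is not shown, so their absence from the protocol is no fault. This disposes of any complaint about the analysis. It does not touch the satisfaction point, which concerns what is collected.

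**Conclusion.** The point holds for satisfaction as a matter of design. Followed as written, the protocol obtains ratings only from people who attend at months 3, 6, 9 or 12, and those ratings may be too favourable. For engagement it holds only as an ambiguity worth closing, with bias arising if sites record usage for attenders alone.

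The 0.05-0.60 point range for satisfaction and the 9-50% range for logins rest wholly on assumed attrition of 10-40% and assumed differences between attenders and non-attenders. The document supplies neither, and zero bias remains possible for both outcomes. This is an inexpensive improvement to a descriptive secondary outcome. It is not an error or contradiction in the plan, and it does not affect the primary outcome.

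**What to change.** In Section 5, add two statements.

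1. Usage logs are exported for every participant who set up the app, through month 12 (the last scheduled visit). Weeks without a login count as zero for as long as the participant is alive and has not withdrawn consent. Without that limit, deaths and withdrawals would be scored as disengagement and the bias would run the other way.
2. The same 1-5 feedback items are sent through the app to participants who miss a visit or stop attending.

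In reporting, give satisfaction with the number responding out of all enrolled, plus a sensitivity bound counting non-responders as not satisfied. The bound needs a cut point on the 1-5 scale, named in advance. As an example with assumed inputs, if 80% of responders are satisfied and 60-90% respond, the bound is 0.80 × 0.60 = 48% to 0.80 × 0.90 = 72%.

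The cost is a data export and an in-app questionnaire. The channel exists, since Sections 8 and 9 already use the app for consent and for returning results. The downsides are that the figures may be less favourable, and that in-app requests will still miss some people who abandoned the app, which is why the bound is needed. The feedback route should be in place before the first follow-up visit, because missed ratings cannot be obtained later.

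### The Baseline Visit does not list the adherence assessment or the quality-of-life questionnaire, so a like-for-like baseline adherence score is not secured and a paired quality-of-life comparison is not possible as scheduled

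*Protocol*

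**What the plan says.** Protocol section 6 defines the primary outcome as guideline adherence, "measured by changes in adherence scores from baseline to 12 months in the variables specified above", with a bracket that limits these to the recommended drugs and lifestyle changes. The variables it points back to are in section 5, under Follow-Up Visits, item 3: "Assess adherence to KDIGO guidelines". That item covers five things:

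- drug treatment, as "prescription including ACE inhibitors and ARBs, SGLT2 inhibitors, GLP-1 analogues, Finerenone and endothelial antagonists";
- blood pressure against the guideline targets;
- diet;
- physical activity;
- "Attendance at medical appointments".

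Item 5 of the same list is the quality-of-life questionnaire. The list is introduced by "Participants will be assessed at 3, 6, 9, and 12 months. At each visit".

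The Baseline Visit list in section 5 has five items of its own: consent; demographics and medical history; blood pressure, creatinine, eGFR, urine ACR and weight, height and BMI; a lifestyle item ("Collect information on lifestyle factors": diet, activity, smoking, alcohol); and help with setting up the app.

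Section 7 gives descriptive statistics and, as the only inferential method, a paired t-test or Wilcoxon signed-rank test of baseline against follow-up. Section 2 includes an objective on the app's impact on quality of life. Section 10 places baseline assessments at month 0 without saying what they are.

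**The concern.** This is a single cohort with no comparator described, so each participant's value before app use is the only reference against which an effect of the app can be seen. Followed as written, the protocol first takes an adherence assessment and a quality-of-life score at month 3, when participants have had the app for three months.

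That leaves two poor choices for the primary analysis. If month 3 becomes the reference by default, any change in the first three months drops out of the comparison. If a baseline score is rebuilt afterwards from the medical history and lifestyle records, values obtained in one way are compared with values obtained in another, and part of the observed change may come from the method of collection. For quality of life even the second choice is closed, because a questionnaire score before app use cannot be recovered later.

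An analysis plan cannot repair this, since it cannot supply data that were not collected. The point therefore belongs in the protocol.

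**Working it through.** The protocol gives no figure to reproduce on this point, so the check sets the two visit lists in section 5 side by side for each follow-up assessment that needs a baseline value.

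| Assessment at months 3, 6, 9, 12 | What the Baseline Visit lists | Status at baseline |
|---|---|---|
| Prescription of the named drug classes | Medical history; medication not named | Uncertain, not itemised |
| Blood pressure control against target | Blood pressure reading | Derivable from raw data |
| Diet | Lifestyle information on diet | Raw data, not assessed for adherence |
| Physical activity | Lifestyle information on activity level | Raw data, not assessed for adherence |
| Appointment attendance | Nothing | Absent |
| Quality-of-life questionnaire | Nothing | Absent |

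**Count for adherence.** Three of the five components have raw baseline data, one is uncertain and one is absent (3 + 1 + 1 = 5). None is listed at baseline as an adherence assessment.

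**Count under a narrow reading of the primary outcome.** The bracket in section 6 limits the variables to recommended medications and lifestyle modifications. Read strictly, that leaves three components: prescription, diet and activity. Two have raw baseline data. The third, prescription, is the one the outcome definition names first, and no baseline item mentions it.

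**Is the omission shorthand?** Probably not. Blood pressure, creatinine, eGFR, ACR and weight, height and BMI are written out in full in both lists. The author repeated what was to be measured at both times and did not repeat the adherence or quality-of-life items. The timeline in section 10 does not fill the gap.

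**Does the analysis need these baseline values?** For adherence, yes: the outcome is defined as a change from baseline. For quality of life the need follows in two steps. The objective concerns the app's impact. With no comparator, impact can only be judged within participants against a value before app use, which is also what the paired tests in section 7 require.

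**Order within the visit.** App set-up is the last baseline item, but section 8 has consent given through the app. A baseline form therefore cannot come before all contact with the app. It can come before the participant starts using the guideline functions, and that is the order that matters.

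**The case against.** The strongest reply is that baseline is not empty. Blood pressure control follows directly from a reading, diet and activity are recorded, and a competent medical history would normally include current drugs. Attendance is neither a medication nor, on a plain reading, a lifestyle modification, so its absence may not touch the primary outcome at all. The quality-of-life outcome in section 6 is not worded as a change.

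All of this stands, and it limits the point. A reader might infer that the adherence change cannot be computed at all. The protocol does not support that: a partial baseline score could be derived. A reader might also infer that a planned change in quality of life has been made impossible. The protocol states no such change. The need for a baseline value is inferred from the impact objective and the general line on paired tests.

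Three further readings are tempting and go too far:

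- That smoking and alcohol form a second gap, because they are recorded at baseline only. The protocol does not expressly name them as outcomes, and recording them once as baseline characteristics is ordinary practice.
- That the loss from using month 3 as the reference can be quantified. The protocol gives no effect size or time course and never proposes month 3 as the reference, so any percentage would rest wholly on assumed inputs.
- That the bias must run towards no change. That needs an early benefit that persists; if an early benefit waned, a month-3 reference could show an apparent decline.

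The reply does not remove the omission itself. Raw diet and activity data are not the same as an assessment against the guideline, prescription rests on an unstated reading of medical history, and nothing at baseline can stand in for a questionnaire score.

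**Conclusion.** The point holds in a limited form. The adherence assessment and the quality-of-life questionnaire are scheduled only after the app is in use, while the primary outcome and the only inferential method both depend on a baseline value.

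- **Adherence:** a baseline score on the same items as at 12 months is not secured, chiefly because prescription is not itemised. Attendance is also missing, if it counts towards the score.
- **Quality of life:** no baseline value is scheduled, so a paired comparison is not possible.

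The conclusion assumes that sites carry out the visit lists as written and that no other source document adds these items at baseline. The effect on the estimate cannot be sized from the protocol, in amount or in direction. The matter should still be settled before enrolment, because the primary outcome depends on it and missing quality-of-life scores cannot be collected afterwards.

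**What to change.** Add follow-up items 3 and 5 to the Baseline Visit in section 5. Have them completed before the participant starts using the app's guideline functions, recognising that consent itself is taken through the app. Use the same items, forms and scoring as at follow-up, and name prescription of the listed drug classes explicitly instead of leaving it to the medical history. The questionnaire should go to the same participants who are to complete it at follow-up.

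For appointment attendance, either use the same look-back window at baseline as at the follow-up visits, which are three months apart, or leave it out of the change score. State which.

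The cost is a change of protocol wording and some extra forms, with the participant and staff time they take, at a visit that already takes place. No extra visit is needed.

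### Follow-up does not record dialysis start, transplant or death, so some patients who reach kidney failure can be scored as improved in the creatinine and eGFR outcome

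*Protocol*

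**What the plan says.** Protocol section 4 admits anyone "Diagnosed with CKD stages 1-5". Its single exclusion is "Inability to provide informed consent due to cognitive impairment", so a patient on dialysis, close to it, or with a transplant may enter.

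Section 2 describes the recommended care as "optimal disease modifying medications to reduce the loss of kidney function and cardiovascular risk over time". Section 6 makes the kidney measurements a secondary outcome: "Changes in clinical parameters (blood pressure, serum creatinine, eGFR, urine ACR").

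Section 5 has "Collect demographic and medical history" at the baseline visit. For follow-up it says "Participants will be assessed at 3, 6, 9, and 12 months". The items listed there are blood pressure, creatinine, eGFR, ACR, weight, height and BMI, then app usage, guideline adherence (prescriptions, blood pressure against target, diet, activity, appointment attendance), feedback on the app, and quality of life. None is an item for dialysis, transplant, death or updated medical history.

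Section 7 compares baseline with follow-up by a paired t-test or a Wilcoxon signed-rank test. It does not say what happens to values obtained after kidney replacement therapy begins.

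**The concern.** In a patient who has started dialysis or received a transplant, creatinine and the eGFR calculated from it no longer measure native kidney function. A working graft filters creatinine and dialysis clears it. If the event is not recorded, such a value enters the paired comparison like any other, and a patient whose own kidneys failed can count in the favourable direction. Patients who die, or who have no later measurement, contribute no pair, and nothing in the listed data says why they are missing.

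Both effects push the result towards apparent benefit. The study has no comparison group in which the same distortion would occur and partly cancel. At stake is the reading of one stated secondary outcome, together with the reader's ability to see how many participants reached kidney failure or died.

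**Working it through.** **1. Is the event captured anywhere?**

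- Entry (section 4): stage 5 is eligible, and dialysis and transplant are not excluded.
- Baseline (section 5): medical history is taken. Existing dialysis or a transplant would ordinarily appear there, though neither is named.
- Months 3 to 12 (section 5): history is not repeated, and there is no item for dialysis, transplant or death.
- Outcomes (section 6): no kidney failure or death outcome. The nearest reference to advanced disease is the conservative care pathway, named only for quality of life.
- Analysis (section 7): paired tests, with no condition on treatment status when the sample was taken.

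Existing dialysis or transplant is therefore probably identifiable, but an event during follow-up is not.

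**2. Which way does each event push the paired difference?**

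Let c0 be baseline creatinine and c2 the follow-up value. The test uses c2 − c0, not the change from the value just before the event.

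- Transplant with a working graft: c2 will usually be below c0 in a patient with advanced disease. This is scored as a gain.
- Dialysis: scored as a gain only if c2 < c0. A patient who worsened from c0 and then started dialysis may still have c2 > c0 and count as a deterioration.
- Death or no later sample: no c2, so no pair.

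The signed-rank test does not remove the problem. A large rise in eGFR receives one of the highest positive ranks.

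**3. How large could it be?**

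The protocol states no figure to reproduce. The values below are assumptions, in mL/min/1.73 m²: d = mean eGFR fall in the other patients (2, 3, 5); g = recorded eGFR rise in the affected patients (5, 20, 40); f = their share of the pairs.

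Mean recorded change = −(1 − f)d + fg. Shift from −d = f(d + g). The mean is zero at f = d/(d + g).

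| d | g | f = 2% | f = 5% | f = 10% | f giving zero |
|---|---|---|---|---|---|
| 2 | 5 | −1.86 | −1.65 | −1.30 | 28.6% |
| 2 | 20 | −1.56 | −0.90 | +0.20 | 9.1% |
| 2 | 40 | −1.16 | +0.10 | +2.20 | 4.8% |
| 3 | 5 | −2.84 | −2.60 | −2.20 | 37.5% |
| 3 | 20 | −2.54 | −1.85 | −0.70 | 13.0% |
| 3 | 40 | −2.14 | −0.85 | +1.30 | 7.0% |
| 5 | 5 | −4.80 | −4.50 | −4.00 | 50.0% |
| 5 | 20 | −4.50 | −3.75 | −2.50 | 20.0% |
| 5 | 40 | −4.10 | −2.75 | −0.50 | 11.1% |

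At f = 2% the shift runs from 0.02 × (2 + 5) = 0.14 to 0.02 × (5 + 40) = 0.90. As a share of the decline, f(1 + g/d), that is 0.02 × (1 + 5/5) = 4% to 0.02 × (1 + 40/2) = 42%. Dialysis patients with c2 > c0 have g < 0 and do not add to the distortion.

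**4. Patients who leave the pairs**

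If a share m has no later value and its mean change would have been −D, the remaining pairs give −d where the full cohort would give −[(1 − m)d + mD]. The difference is m(D − d), which favours the result whenever those lost declined faster (D > d). This is also why discarding post-event values is not a sufficient remedy.

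**The case against.** The opposing case has force on several points.

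- *The follow-up list is wider than laboratory values.* True. It covers prescriptions, appointments, feedback and quality of life, and such contacts may reveal a dialysis start by chance. None of them is a field for it.
- *Baseline history would show existing dialysis or a transplant.* Largely accepted. The gap concerns new events, and at baseline the item needs only to be made explicit.
- *Dialysis need not look like improvement.* Accepted. A reader might infer that every case of kidney failure is analysed as a gain. The paired test compares with the patient's own baseline, so this holds for on-dialysis values only when creatinine is below that baseline. Death gives no value and cannot be scored as improvement.
- *The effect may be negligible.* Possible. With few stage 4 and 5 patients the mean may barely move. A reader might infer from unfavourable assumptions that the whole decline could be hidden, but the protocol offers no event rate to support or exclude that.
- *No safety outcome is lost.* Accepted. The protocol names none, and the phrase about kidney function in section 2 describes the purpose of the recommended care, not an endpoint.
- *Handling of post-event values belongs in a statistical analysis plan.* Partly accepted. An analysis plan not shown here may hold such a rule, but it could not identify the affected values from the data that the protocol lists. Section 7 also says all data will be anonymised. If that is literal, going back to hospital records later may be impossible.

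**Conclusion.** The point stands for events during follow-up. The protocol admits patients who can reach kidney failure within the study, feeds their later creatinine, eGFR and ACR into paired tests, and collects nothing that would mark the affected values or explain the missing ones. Values after a transplant, and some values on dialysis, would be scored as improvement. Deaths and other losses would be invisible.

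The direction rests on how creatinine behaves after a transplant or on dialysis and on the paired comparison that the protocol specifies. The size rests wholly on assumed values: at a 2% share the mean eGFR change shifts by 0.14 to 0.90 mL/min/1.73 m², and the share that brings the mean to zero lies between 4.8% and 50%. No estimate specific to this study is possible without a sample size, stage mix or event rate.

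The consequence is confined to a secondary outcome, and the primary adherence score is not affected by this point. The change is worth making because it is cheap and the information may not be recoverable afterwards.

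**What to change.** - **Baseline:** name dialysis and transplant status explicitly within the medical history.
- **Months 3, 6, 9 and 12:** record from the clinical record the date of any dialysis start, transplant or death. This must happen while participants can still be linked to that record.
- **Analysis set:** limit the creatinine, eGFR and ACR change outcomes to participants not on dialysis at baseline.
- **Values after the start of kidney replacement therapy:** do not read them as change in native kidney function. Since dropping them would remove the worst patients, count these participants as kidney failure, for example by ranking them as the worst change in the signed-rank comparison of eGFR.
- **Reporting:** give the numbers with kidney failure and death beside the mean changes, so that it is clear whom the means leave out.

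The cost is a few dated fields on the visit form and a sentence in section 7. The reported kidney-function changes may look less favourable. No additional visits or tests are needed.

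### The quality-of-life objective covers CKD patients, but the Section 6 outcome meant to answer it covers only an undefined conservative-care group of unknown size

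*Protocol*

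**What the plan says.** Four parts of the Protocol bear on who contributes to the quality-of-life outcome.

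- **Section 2, Secondary Objectives:** "To determine the impact of the application on the quality of life of CKD patients". No subset is named.
- **Section 4, Study Population:** the disease criterion is "Diagnosed with CKD stages 1-5", and the only exclusion is "Inability to provide informed consent due to cognitive impairment". Care pathway is not a criterion in either list.
- **Section 5, Follow-Up Visits, item 5:** quality of life is to be measured at each follow-up visit (3, 6, 9 and 12 months) in patients, with a validated questionnaire. No pathway is mentioned. The Baseline Visit list contains no quality-of-life questionnaire.
- **Section 6, Secondary Outcomes:** "Quality of life assessed in patients being managed as part of the conservative care pathway", with the same example questionnaire as in Section 5.

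The analysis in Section 7 is "Paired t-tests or Wilcoxon signed-rank tests to compare baseline and follow-up measurements". It names no subgroup and does not define the pathway.

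**The concern.** An outcome should be measured in the population its objective asks about. Here the objective is broad and the outcome is narrow, and nothing in the Protocol explains the narrowing.

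Two analysts could each claim to follow the Protocol and report different results. One working from Section 2 would analyse every enrolled participant. One working from Section 6 would analyse the conservative-care group alone. Unless the choice is settled beforehand, it could be made after the data have been seen.

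The narrow version also depends on a classification that the Protocol does not define and does not explicitly collect. Pathway status is not a listed baseline item, although the medical history might capture it. No time point is attached to membership, so the set of patients entering a paired comparison is not fixed.

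This is not detail that can be left to a statistical analysis plan. The Protocol does say whom the outcome covers, and it says so in conflicting ways.

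**Working it through.** The Protocol states no figure on this point, so the check is a comparison of texts.

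**Step 1: population by section**

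| Place | Population for quality of life | Restricted to the pathway? |
|---|---|---|
| Section 2, objective | CKD patients | No |
| Section 4, eligibility | CKD stages 1 to 5, able to consent | No |
| Section 5, follow-up item 5 | Patients | No |
| Section 6, outcome | Patients on the conservative care pathway | Yes |

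**Step 2: could the wordings mean the same thing?** They would coincide only if every participant were on the pathway. Section 4 does not require that. Sections 5 and 6 are close to identical sentences. Section 5 has "Quality of life assessed in patients using a validated questionnaire (e.g., POS-S-Renal", and Section 6 inserts the pathway restriction into the same sentence. Either the insertion does not belong, or Sections 2 and 5 are too broad. Both cases need a correction.

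**Step 3: how many participants are affected?** With N enrolled and a share s on the pathway, Section 6 covers s × N participants and leaves (1 − s) × N outside. The Protocol gives neither N nor s, so neither count can be derived.

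**Step 4: what would precision depend on?** If the standard deviation of the score change were the same in the subgroup as in the whole cohort (an assumption), the standard error of the mean change would grow by 1/√s. For assumed shares:

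- s = 0.05: 1/√0.05 = 4.5
- s = 0.20: 1/√0.20 = 2.2
- s = 0.80: 1/√0.80 = 1.1

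The range runs from a severe loss of precision to almost none, and the Protocol does not say where the study lies in it. The mismatch of populations is present at any share below 100%.

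**Step 5: can a change from baseline be computed at all?** Section 7 pairs baseline with follow-up. Items 1 to 5 of the Baseline Visit cover consent, history, clinical measurements, lifestyle factors and application set-up. None is a quality-of-life score. As written, the first listed score is at 3 months, after the application has been set up. The paired comparison therefore has no listed baseline in either population, and rewording Section 6 alone would not supply one.

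**The case against.** The strongest reply is that Section 5 says patients, not all patients, and may be shorthand for the group in Section 6, since the two share the same questionnaire phrase. On that reading only conservative-care patients complete the questionnaire, and the defect shrinks to an objective broader than its outcome. The reading is possible, and for that reason no claim is made here that collected questionnaires would be thrown away. It does not remove the problem: the Section 2 objective would still go unanswered outside the pathway, and the pathway would still be undefined.

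Three stronger inferences are tempting, and the Protocol does not support them.

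- **That the subgroup is small.** This may seem plausible in a stage 1 to 5 cohort, but an undefined group cannot be sized. Under a broad meaning of the term it could be most of the cohort.
- **That a given percentage of questionnaires goes unused.** This needs the pathway's share, which is not stated, and also needs Section 5 to mean every participant.
- **That patients move on or off the pathway during follow-up.** The Protocol says nothing about such transitions. It can only be said that no time point for membership is given.

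It is also fair to say that this is one secondary outcome in a study with simple paired analyses. That limits the weight of the point but does not remove the contradiction.

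**Conclusion.** The point holds as a conflict between Sections 2, 5 and 6 over the population for quality of life. As written, the Section 6 outcome cannot answer the Section 2 objective for any participant outside the conservative care pathway. The number of such participants is unknown, and no loss of data or precision can be put on it from the Protocol. The conclusion rests on the wording alone and needs only one assumption: that not every enrolled participant is on the pathway, which the eligibility criteria leave open.

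A linked gap is that no baseline quality-of-life score is listed, so any remedy expressed as change from baseline needs an added assessment. The matter should be settled before analysis; a population chosen once results are known would be hard to defend.

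**What to change.** Preferred route:

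1. In Section 6, define the outcome as change in the questionnaire score from baseline to 12 months (the last scheduled visit) in all enrolled participants.
2. In Section 5, add the same questionnaire to the Baseline Visit, and make follow-up item 5 say explicitly that it applies to all participants.
3. Define the conservative care pathway, record each participant's status at baseline, and report that group as a subgroup.

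Alternative, if only the conservative-care group was intended: narrow the Section 2 objective and Section 5 item 5 to that group, and define the pathway by status at baseline. The baseline questionnaire is still needed, for that group, if the paired comparison in Section 7 is to be made.

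Cost: protocol wording, plus one questionnaire and one status item at the baseline visit. For participants who already have the application, a baseline score cannot be recovered afterwards, so the addition should be made before or early in enrolment.
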